## **BACKGROUND**

---

Cleft lip and palate (CLP) is one of the most common congenital abnormalities in the UK with an estimated prevalence of 1 in 700 live births (1, 2). Prevalence varies by ethnicity, geographic origin and gender with males more likely than females to have a unilateral cleft lip and palate (UCLP)(3). In addition a left-sided cleft is more common than a right sided cleft (4). Care of a person with cleft lip and palate is complex. It usually begins with antenatal diagnosis and continues into adulthood. Treatment of cleft lip and palate is resource intensive requiring evaluation and care from a range of specialists including Audiologists, Cleft Nurse Specialists, Clinical Geneticists, Clinical Psychologists, Dieticians, Orthodontists, Medical Photographers, Paediatricians, Paediatric Dentists, Restorative Dentists, Speech and Language Therapists, and Surgeons (from ENT, Plastic Surgery, and Maxillofacial Surgery) to achieve the optimum outcome.

In the 1990s concerns were expressed over the standard of care and outcome in children with cleft lip and palate in the United Kingdom (UK) and the training of those health care professionals providing it (5-8). These concerns led the Clinical Standards Advisory Group (CSAG), to commission a national survey of the care and outcome in children with CLP – referred to in this document as the CSAG survey (9, 10). This survey began in 1996 and ran over a 15 month period. The survey aimed to include all non-syndromic children in the U.K., born with a complete UCLP aged either 5 or 12-years of age. The outcomes assessed included the quality of speech, hearing, naso-labial appearance, dental arch relationships, oral health, the success of alveolar bone grafts (in the 12 year old cohort only) and child/parent satisfaction (11-14).

In 1998 the group published their main report (1). Fifty seven centres were identified as providing a cleft service in the U.K. with the number of cases being treated per year varying considerably. They found that the outcomes of cleft care in the U.K. were generally poor. One of the key findings was the poor outcome with respect to dental arch relationships and profile, when compared with three European centres (Oslo, Bergen, and Nantes). It was reported that 36% of 5 year olds and 39% of 12 year olds with UCLP had a poor dental arch relationship. Other centres in Europe have shown outcomes with less than 10% of UCLP cases having poor dental arch relations (1).

On the basis of this survey it was concluded that some children with CLP were not receiving optimal care in the UK. The group made nine recommendations to the government all of which were accepted (Appendix 1). The acceptance of these recommendations led to a major reorganization of cleft services across the UK, with the concentration of resources and expertise in fewer units. Current arrangements have configured eleven cleft centres carrying out operations at seventeen cleft sites in the UK working within multi-disciplinary teams.

The overall aim of the current study is to evaluate the impact of this service reorganization on the standard of care currently provided for, and the outcomes achieved in, children with cleft lip and palate in the UK. Centralisation of care in a smaller number of larger centres has important resource and logistic implications for both users and service providers and this study will attempt to estimate the cost and cost effectiveness of the changes in cleft care. The work is funded by a NIHR grant "Evidence based health care for major congenital and acquired problems of the head and neck", Reference Number: RP-PG-0707-10034.

## **OBJECTIVES**

---

1. To describe the care currently provided for five year old children with UCLP and to compare this to that care originally described in the CSAG survey.
2. To describe the outcomes in five year old children with UCLP and compare this to the outcomes described in the original CSAG survey.
3. To estimate the economic impact of the centralisation of cleft care services.
4. To estimate the personal costs to parent/guardian and families of children with UCLP.
5. To quantify preferences for different attributes of centralised cleft care from the perspective of parents/guardians of children born with UCLP.

## **RESEARCH MANAGEMENT**

---

### **SAFETY REPORTING**

---

As this is an observational study we are only collecting adverse events directly related to study related procedures according to U H Bristol Research Adverse Event Policy.

### **MONITORING AND AUDIT**

---

The study will be monitored and audited in accordance with Trust policy. All study related documents will be made available on request for monitoring and audit by UH Bristol and the relevant Research Ethics Committee.

### **DATA PROTECTION**

---

Data will be collected and retained in accordance with the Data Protection Act 1998.

## STORAGE OF RECORDS

---

Study documents (paper and electronic) will be retained in a secure location during & after the study has finished. At the end of the study, all paper study documents will be scanned and then electronically stored on a NHS secure encrypted hard disk. All source documents will be retained for at least 25 years following the end of the study.

## INDEMNITY

---

This is an NHS-sponsored research study. For NHS sponsored research HSG(96)48 reference no. 2 refers. If there is negligent harm during the study when the NHS body owes a duty of care to the person harmed, NHS Indemnity covers NHS staff, medical academic staff with honorary contracts, and those conducting the study. NHS Indemnity does not offer no-fault compensation and is unable to agree in advance to pay compensation for non-negligent harm. Ex-gratia payments may be considered in the case of a claim.

## ETHICS & R&D APPROVALS

---

The study will be performed subject to Research Ethics Committee (REC) approval, including any provisions of Site Specific Assessment (SSA), and local Research and Development (R&D) approval.

## RESEARCH GOVERNANCE STATEMENT

---

This study will be conducted in accordance with the Research Governance Framework for Health and Social Care and Good Clinical Practice.

## CONSULTATIONS

---

### PLANNED

---

Visit Oxford Cleft Service	23 April, 2010
Visit Northwest and North Wales Cleft Centre	27-28 April, 2010
Visit Salisbury Cleft service	7 May, 2010
Visit Trent Cleft Service	24May, 2010

We plan to visit all Cleft centres before the CSAG II commences on the 1st of July 2010.

**TIME TABLE**

---

Draft protocol for circulation	December 2009
Identification of eligible cases	November 2009- January 2010
Visits to cleft centres	December 2009 – June 2010
Submit ethics application	April 2010
Meet with R&D contacts (support costs)	January - March 2010
Staff training days for research clinic	January -June 2010
Cleft workshop	4-5 March 2010
5 year old survey	July 2010 – December 2012

## **ASSESSMENT OF PREFERENCES FOR DIFFERENT ATTRIBUTES OF CENTRALISED CLEFT SERVICES**

---

### **RATIONALE**

---

In the past few years, the NHS has been increasing its efforts in raising patient and public involvement in the delivery of health and social care services. As the process of centralisation of cleft services throughout the U.K. has developed at different rates and different models of centralised care have emerged, one of the ways to evaluate the re-organisation of this service is to quantify the relative value of different attributes of this service from the perspective of parents/guardians of children with unilateral cleft lip and palate (UCLP). The data collected would provide useful information in the delivery of cleft services to optimise outcomes within a given budget.

A discrete choice experiment (DCE) using best-worst scaling (15) will be used to estimate the relative value of different attributes of centralised cleft care services. This method is made up of five stages (16). The first stage involves the identification of attributes and this will be done through a review of the literature, and semi-structured qualitative interviews with parents/guardians of children born with UCLP. The second stage entails the assignment of levels to the characteristics identified which should be plausible and actionable, and this will be explored with parents/guardians during the semi-structured interviews. Where applicable, local and national standards, e.g. with reference to waiting times, will be incorporated into the development of levels for each attribute. The third stage involves the choice of scenarios that would describe the possible service (or outcome) configurations based on the attributes and

levels chosen. An experimental design will be used to establish a manageable number of scenarios. The last two stages cover the collection of data and data analysis.

## STUDY SAMPLE

---

### **Preliminary semi-structured qualitative interviews**

Potential study sample will be parents/guardians of children with UCLP. These parents/guardians will be purposively selected with the aim of sampling for maximum variation in terms of their geographical location within the UK, and travelling distances between their homes and the cleft service administrative sites where their children receive care. Sample size for this part of the study will be determined by data saturation.

### **Discrete Choice Experiment (DCE)**

Parents/guardians of children with UCLP will be asked to take part in the DCE. It is likely that there will be at least two potential subgroups of parents/guardians who may have different preferences: those who live within a short distance from their local cleft centre (i.e. within 30 miles), and those who live a long way from their local cleft centre (i.e. exceeding 30 miles). This will be confirmed through the interviews with parents/guardians. Other possible subgroups will be explored through the same semi-structured interviews. The sample size for each subgroup in a DCE is usually set between 30 and 100 individuals (16). The aim will be to achieve, on average, a sample of 30 individuals per subgroup (i.e. at least 60 participants in total or more if more subgroups were identified). Recruitment of parents/guardians will continue until at least 60 (or more if necessary) completed responses have been achieved.

## SETTING

---

### **Preliminary semi-structured qualitative interviews**

Given that participants will be drawn from across the UK, it will be most practical to conduct these interviews by telephone.

### **Discrete Choice Experiment**

The DCE questionnaire will be distributed in two ways:

- a) For parents/guardians of children already recruited into the study and who have consented to be contacted again, the questionnaire will be posted to them.
- b) For parents/guardians of children who will be prospectively recruited into the study, they will be asked at the end of the clinic audit day if they would like to take home and complete the questionnaire (together with the Health and Lifestyle questionnaire).

## IDENTIFICATION OF ELIGIBLE PARTICIPANTS

---

### **Preliminary semi-structured qualitative interviews**

A request will be sent to each clinical director for their help in providing a potential list of four parents/guardians: two who live near to the cleft service administrative site, and two who live a long distance away from the site. These would be parents/guardians of 5 year old children who have already attended the audit clinics at their local cleft centre for the time period 01/09/09 – 31/05/2010 and consequently is not part of the CSAG II project.

### **Discrete Choice Experiment**

Both parents/guardians of children already recruited into the study and who have consented to be contacted again as well as those who will be prospectively recruited into the study will be invited to take part.

---

## INCLUSION CRITERIA

---

For both parts of the research, informed consent to participate is essential. In addition,

- a) For the preliminary semi-structured qualitative interviews, parents/guardians of children with UCLP who have already attended the audit clinics at their local cleft centre when they were 5 years old will be included into the potential list of participants.
- b) For the DCE, parents/guardians of children with UCLP who have or are attending the audit clinic at their local cleft centre when they are aged 5 years old will be invited to participate.

## EXCLUSION CRITERIA

---

The aim is to obtain a wide-ranging perspective from parents/guardians and hence no exclusion criteria have been set. Individual cases will be checked for suitability to participate based on the inclusion criteria.

## PROCESS

---

### **Preliminary semi-structured qualitative interviews**

An email will be sent to all clinical directors requesting each of them to provide a potential list of four parents/guardians: two who live near to the cleft service administrative site, and another two who live a long distance away from the site.

Initially, ten parents/guardians from each of the two subgroups will be purposively selected and contacted by letter (together with an information leaflet, a consent form and a reply slip) (Appendices 2 to 5) asking for their consent to participate in the research. These letters will be sent via the hub centre. Upon receipt of signed consent forms, a member of the research team

will contact each individual by telephone to arrange for a convenient time to conduct the semi-structured interview by telephone.

If, after contacting all the parents/guardians on the initial list, no parents/guardians agree to participate, the cleft centres will be approached again for help to provide further names of parents/guardians.

Once all interviews, which will be taped, have been conducted, the qualitative data will be transcribed and analysed in order to develop the DCE questionnaire.

### **Discrete Choice Experiment**

#### **i) Parents/guardians of children already recruited into the study and who have consented to be contacted again:**

A copy of the DCE questionnaire together with a cover letter and an information leaflet will be posted to them. They will be asked to complete the questionnaire and mail it back to the researchers within a week. If the questionnaire is not returned within 7-14 days, the research team will mail out another questionnaire together with a FREE POST envelope asking them to complete the questionnaire. Half of the group will receive version 1.5a of the DCE questionnaire and the other half will receive version 1.5b of the questionnaire.

#### **ii) Parents/guardians of children who will be prospectively recruited into the study**

Currently, this group of parents/guardians are being asked at the end of the research audit clinic day if they would like to take home and complete a health and lifestyle questionnaire. The DCE questionnaire will be added to this to form a questionnaire pack. If they agree to complete the questionnaire pack, they will be given the pack together with a information leave and FREE

POST envelope. They will be asked to return the completed questionnaires to the researcher within one week. If the questionnaires are not returned within 7-14 days, the research team will mail out another questionnaire pack together with a FREE POST envelope asking them to complete the questionnaires. Half of the group will receive version 1.5c of the DCE questionnaire and the other half will receive version 1.5d of the questionnaire.

The complete version of the DCE questionnaire contains 17 choice questions of which 16 are derived from a fractional factorial experimental design and one is a test for internal consistency. In order to minimise participant's fatigue due to having to complete 17 choice questions, the questionnaire has been divided into 2 versions (see DCE questionnaire version 1.5a and version 1.5b). Each version is made up of 9 choice questions, i.e. half of the 16 derived from the experimental design and the test for internal consistency question. Version 1.5a will be abridged to exclude some background questions that have already been included in Health and lifestyle questionnaire and become version 1.5c. Likewise, version 1.5b will be abridged and become version 1.5d.

## OUTCOME MEASURES

Data from the DCE based on best-worst scaling will be analysed using weighted least squares. The results will demonstrate the relative value of the different attributes that parents/guardians of children born with CLP place on cleft services.

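### The preference study names weighted least squares as its only analysis without allowing for the 8 design answers each parent gives, so its usual standard errors would probably be too small

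*Protocol*

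**What the plan says.** All of this is in the protocol's chapter on preferences for attributes of centralised cleft services.

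- **Analysis (Outcome Measures).** "Data from the DCE based on best-worst scaling will be analysed using weighted least squares". The promised output follows: "The results will demonstrate the relative value of the different attributes". No interval, test or significance level is given for the DCE.
- **Questions per parent (Process, Discrete Choice Experiment, part ii).** "The complete version of the DCE questionnaire contains 17 choice questions of which 16 are derived from a fractional factorial experimental design", and the questionnaire is split in two: "Each version is made up of 9 choice questions, i.e. half of the 16 derived from the experimental design and the test for internal consistency". Each parent therefore sees 8 design questions and one consistency question.
- **Sample (Study Sample, DCE).** "It is likely that there will be at least two potential subgroups of parents/guardians who may have different preferences", namely those living within 30 miles of their centre and those living further away. "The aim will be to achieve, on average, a sample of 30 individuals per subgroup", which makes at least 60 in total.
- **Elsewhere.** The Statistical Analysis section plans multi-level models for variation across centres. It does not deal with repeated answers from one parent in the DCE.

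**The concern.** The sampling unit is the parent and the unit of measurement is the choice. Parents with different priorities give answers that resemble one another within a parent, so precision depends on the number of parents as well as the number of choices. The protocol anticipates that preferences may differ between near and far families. Further variation among parents within each group is not stated, but it is a natural assumption.

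In its usual form for best-worst data, weighted least squares (WLS) is run on choice frequencies pooled over respondents. Once pooled, the data no longer show which answers came from the same parent. That reading of the method is an inference, because the protocol does not describe the data layout.

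This is the only analysis named for objective 5, and the chapter's rationale wants the results to inform how services are delivered within a budget. Standard errors that are too small would make attribute values look better known than they are. They would also make chance differences between attributes, or between near and far families, look real.

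**Working it through.** **1. The plan's own figures.** 16/2 + 1 = 9 questions per version, 8 of them from the design. 2 × 30 = 60 parents. Both agree with the protocol. Thirty parents give 30 × 8 = 240 design answers.

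**2. Design effect as a guide.** With m = 8 answers per parent, DE = 1 + (8 − 1) × ICC. The true standard error (SE) is √DE times the naive one. Actual coverage of a nominal 95% interval is 2Φ(1.96/√DE) − 1, and the false-positive rate of a nominal 5% test is its complement. The documents give no ICC, so the values are assumed.

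| ICC | DE | Effective answers of 240 | True/naive SE | Coverage | False positives |
|---|---|---|---|---|---|
| 0 | 1.00 | 240 | 1.00 | 95% | 5% |
| 0.02 | 1.14 | 211 | 1.07 | 93.4% | 6.6% |
| 0.05 | 1.35 | 178 | 1.16 | 90.8% | 9.2% |
| 0.10 | 1.70 | 141 | 1.30 | 86.7% | 13.3% |
| 0.20 | 2.40 | 100 | 1.55 | 79.4% | 20.6% |
| 0.30 | 3.10 | 77 | 1.76 | 73.4% | 26.6% |

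The SE ratio does not change with the number of parents. The formula assumes equally correlated answers, so it is a guide and not a model of best-worst data.

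**3. Simulation of attribute values.** WLS was fitted to log counts of best-worst pairs (0.5 added to each count). Assumed: 5 attributes with 4 levels each, 16 profiles in two blocks of 8, and 400 runs per setting. The table shows the empirical standard deviation of the estimates divided by the reported SE. A value above 1 means that the reported SE is too small.

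| Parents | SE used | No preference differences | With preference differences |
|---|---|---|---|
| 60 | Residual-based | 1.04 | 1.16–1.38 |
| 30 | Residual-based | 1.15 | 1.31–1.48 |
| 60 | Fixed-scale | 0.77 | 0.85–1.02 |
| 30 | Fixed-scale | 0.74 | 0.84–0.97 |

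The 1.15 at 30 parents arises with no clustering at all and reflects sparse counts. The share due to differences between parents is 1.16/1.04 = 1.12 to 1.38/1.04 = 1.33 with 60 parents, and 1.31/1.15 = 1.14 to 1.48/1.15 = 1.29 with 30.

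**4. Simulation of a near-versus-far contrast with no true difference.** Assumed: 30 versus 30 parents, the same 5 × 4 layout and 1,000 replicates per setting. The false-positive rates at a nominal 5% were:

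| ICC | WLS on log pair counts | Conditional logit, respondent-clustered SE |
|---|---|---|
| 0 | 9.6% | 5.6% |
| 0.05 | 13.8% | 4.1% |
| 0.09 | 16.3% | 4.9% |
| 0.20 | 18.8% | 4.2% |

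The 9.6% at ICC 0 comes from empty pair cells (about 47% are empty with 30 parents under these assumptions). The part due to repeated answers is 13.8 − 9.6 = 4.2 points at ICC 0.05 and 18.8 − 9.6 = 9.2 points at 0.20.

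A second simulation of the same 30 versus 30 contrast was milder. Residual-based errors gave about 8–9% without differences between parents and 10–12% with them. Fixed-scale errors gave about 0–2%, which is too conservative.

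**The case against.** The strongest reply is that WLS names an estimator and not a variance method. It is compatible with a bootstrap by respondent, and an analysis plan that is not shown may specify one. The protocol promises relative values only. It states no interval and no near-versus-far test, and it uses the distance subgroups to set the sample size. The ICC and the attribute layout in the working are assumptions. The simulated contrast also uses the minimum sample: recruitment may go beyond 60, and the survey from which parents are invited expects at least 250 children. More respondents would reduce the empty-cell problem.

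Much of this stands, and it rules out several stronger readings that a reader might infer:

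- **That the plan treats answers as independent, or counts 30 parents as 240 observations.** It says neither. It is silent on how repeated answers are handled.
- **That the intervals are certainly too narrow.** That depends on the variance used. With a fixed scale, SEs for attribute values were essentially not too small, and the contrast test was conservative.
- **That the whole simulated excess is due to repeated answers.** Part of it is sparse cells.
- **That WLS is inadmissible or its attribute values biased.** Nothing here shows that.

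The reply does not remove the practical point. The protocol fixes a method whose usual standard errors were miscalibrated at 30 parents per group in these simulations: too small on the residual basis, mostly too large on the fixed-scale basis. Neither reflects the respondent. Sizing by distance subgroup also implies that the groups will be compared, even though no test is written down.

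**Conclusion.** The point holds as a conditional one. The protocol names a single DCE analysis and does not allow for 8 design answers per parent, although the sample is counted in parents and preferences are expected to vary. If residual-based WLS standard errors are used, intervals for attribute values and for any near-versus-far comparison will probably be too narrow.

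The size cannot be fixed from the documents. By the design-effect guide, the true SE is 1.16 times the naive one at an assumed ICC of 0.05 and 1.55 times at 0.20, with no loss at 0. In the attribute-value simulation, differences between parents accounted for a factor of about 1.1 to 1.3. These figures rest on assumed correlations, an assumed 5 × 4 attribute layout and an assumed pooled form of WLS. Point estimates of relative value are unaffected by this argument. It is an inexpensive improvement to the plan, not a demonstrated error in its results.

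**What to change.** Add to the DCE Outcome Measures paragraph a statement that uncertainty will be computed at respondent level, in one of two ways:

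1. Keep WLS for the point estimates and take confidence intervals from a bootstrap that resamples whole respondents within questionnaire version.
2. Fit a best-worst conditional logit model with standard errors clustered on the respondent.

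State also that any near-versus-far difference will be tested with the same respondent-level variance, for example as attribute-by-distance interactions in the logit model. The second option held its false-positive rate at 4.1% to 5.6% in the contrast simulation above. The bootstrap was not simulated.

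The cost is about a sentence of text and a little more analysis work. No new data are needed, because each returned questionnaire is already one respondent's record. Intervals may be wider than the default WLS ones.
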